1.0 Objectives

1.1 Study Objectives

The long term objective of this study is to determine whether Pioglitazone (PGZ) can improve clinical outcomes in hyperglycemic acute ischemic stroke (IS). We propose to study the efficacy of PGZ treatment and its effects on the peripheral immune-stress response in hyperglycemic stroke patients within a randomized, placebo controlled, double-blinded clinical pilot study with two objectives:

- 1. Study the effects of acute PGZ treatment on clinical outcomes at three months after stroke:** Well validated assessment tools of neurological function, including the NIH Stroke Scale (NIHSS), modified Rankin scale (mRS), Barthel index (BI) and Glasgow Outcome Scale (GOS) will be used to assess neurological outcomes. In addition, cognitive function will be assessed by the Montreal Cognitive Assessment (MOCA), and data on in-hospital and after discharge infection rates, re-hospitalization rates, stroke volume and all-cause mortality will be collected.
- 2. Explore whether acute treatment with PGZ can improve outcomes in hyperglycemic stroke by modulation of the stress-immune response.** We will measure how PGZ changes blood concentrations of insulin, glucose, cortisol and catecholamines after initiation of treatment. Based on our preliminary preclinical studies, we hypothesize that PGZ will decrease circulating levels of activated neutrophils and monocytes, improve neutrophil function, decrease cytokine levels, normalize the N/L ratio and increase the anti-inflammatory annexin A-1 pathway, all of which are altered in the hyperglycemic state.

1.2 Primary Study Endpoints

The primary objectives of this pilot study are 1) to determine whether PGZ can improve outcomes at 3 months post-stroke in hyperglycemic acute ischemic stroke, and 2) to study whether there is association between immune-stress response modulation and clinical outcomes after treatment of PGZ following acute ischemic stroke in hyperglycemic patients.

1.3 Secondary Study Endpoints

- 1) To examine the impact of PGZ on the stress-immune response by measuring cortisol, epinephrine, norepinephrine levels and inflammatory mediators in hyperglycemic ischemic stroke patients.
- 2) To study the correlation between clinical outcomes and pro and anti-inflammatory mediators after acute treatment of PGZ in hyperglycemic patients.
- 3) To study the effects of PGZ on stroke volume, cerebral edema and hemorrhagic conversion measured on brain magnetic resonance imaging (MRI) and /or head computed tomography (CT).

2.0 Background

2.1 Scientific Background and Gaps

The global burden of stroke and diabetes is substantial and steadily growing. Stroke-related health care expenditures are projected to increase from \$17.5 billion in 2000 to \$30.3 in 2030 [1]. Stroke is the second leading cause of death in the diabetic population and the most common cause of chronic disability. A review of our institutional stroke database revealed that about 50% of all acute stroke patients have diabetes or hyperglycemia who have a glucose level of ≥ 150 mg/dl which corroborates observations from previous studies [2]. This high prevalence has far ranging implications for acute stroke care, as patients with diabetes and hyperglycemia have worse clinical outcome, higher mortality rates, more severe disability, larger infarct size, and greater risk for recurrent stroke [3]. The confluence of these effects will result in a dramatic increase in the annual stroke frequency, currently standing at 5.8 million in the U.S., within the next 25 years [4].

In humans and in animals, IS causes an acute stress-immune response through activation of the sympathetic nervous system and the hypothalamic-pituitary axis leading to the release of cortisol and catecholamines [5-7]. Elevated cortisol and catecholamine levels deplete circulating lymphocytes, induce leukocytosis and activate neutrophils which then migrate into the site of brain injury, where they release mediators of inflammation and cause tissue damage. They also undergo apoptosis and become cleared by phagocytosis, which is important for the initiation of tissue repair [8, 9]. Cortisol can have opposing effects on neutrophil apoptosis and subsequent tissue fate. It can induce the release of annexin A1 from neutrophils, which will then bind to their surface receptors, causing neutrophil apoptosis and inhibition of neutrophil extravasation into the infarcted area, downregulating the extent of inflammation [10]. On the other hand, cortisol can increase anti-apoptotic factors such as Mcl-1 and decrease pro-apoptotic molecules, leading to prolonged neutrophil survival and upregulation of the inflammatory response [11, 12].

By reducing circulating lymphocytes, suppressing the T-cell response and inhibiting monocytes, eosinophils and various other components of the innate and adaptive immune response, cortisol and epinephrine also render the host more susceptible to infection, contributing to complications and increased stroke morbidity and mortality [13, 14]. Previous studies have shown that an increase in the peripheral neutrophil to lymphocyte (N/L ratio) after an acute IS is correlated with worse clinical outcome [15, 16].

2.2 Previous Data

Our preliminary data from 24 acute IS patients showed that hyperglycemic (glucose level $\geq 150\text{mg/dl}$) stroke patients had significantly higher cortisol levels and more pronounced and earlier peripheral neutrophil activation than their euglycemic counterparts, suggesting an alteration of the post-stroke stress-immune response in the hyperglycemic state. Similarly, in our preclinical studies of diabetic db/db mice, the extent of brain damage after IS was significantly worse in diabetic compared to euglycemic animals [13]. In our preclinical and clinical pilot studies, we observed that the peripheral N/L-ratio was higher in hyperglycemic compared to euglycemic stroke patients and in diabetic compared to non-diabetic mice. In stroke patients, an increased N/L ratio was associated with higher rates of malignant cerebral edema, worse neurological function and greater neurological disability, irrespective of i.v. t-PA use. In addition, hyperglycemic patients showed a more pronounced peripheral lymphocyte suppression for B- and T-lymphocytes, including T-helper, T-suppressor and natural killer cells.

We have previously shown the importance of neutrophils for stroke outcomes where neutrophil depletion prior to induction of IS in db/db mice resulted in significantly smaller stroke volumes. Thus, an intervention aiming at restoration of the altered stroke-induced immune response is a promising approach to improve outcome in hyperglycemic stroke. We have demonstrated that darglitazone, that is a similar drug within the same class and similar mechanism of action, restores the altered pro-inflammatory response and dramatically reduces stroke size in diabetic ob/ob mice when administered before IS was induced [13]. In addition, PGZ given to non-diabetic C57BL6 mice within 2h after acute IS, also reduced the stroke size and the inflammatory response at the site of brain injury. After administration of a single dose of 30/mg/kg (which is equivalent to approximately 150 mg dose in humans) of PGZ immediately after IS, we observed a significant decrease in circulating neutrophils and an increase in lymphocytes at 4h and 24 h compared to baseline, and smaller stroke volumes in PGZ versus placebo (saline) injection-treated mice. Furthermore, we found a decrease in astrocyte and microglia activation following PGZ treatment, suggesting a reduced central inflammatory response. In summary, our preliminary results suggest that the post-stroke stress-immune response is altered in diabetes and that PGZ may improve clinical outcome by modulating this response.

2.3 Study Rationale

The rationale for the proposed research is to develop an acute intervention that can improve neurological recovery and decrease mortality and morbidity in hyperglycemic stroke patients who are a high risk group for poor outcome. Understanding how the immune-stress response is altered in hyperglycemic stroke and how PGZ may modulate this response is an entirely novel undertaking. If PGZ shows a trend towards efficacy and the study design proves feasible, we aim to conduct a multi-center trial of PGZ in acute hyperglycemic stroke patients.

3.0 Inclusion and Exclusion Criteria

3.1 Inclusion Criteria

To be eligible to participate in this study, candidates must meet the following eligibility criteria at screening:

1. Aged 21 or older
2. Diagnosis of acute IS
3. Must present within 18 hours of stroke symptom onset or within 18 hours of their last known time being well.
4. Blood glucose level greater than 150 mg/dl at the time of presentation.
5. Brain MRI or head CT proven ischemic stroke or clinical presentation suggestive of IS.
6. Initial NIH SS of ≥ 2 .

3.2 Exclusion Criteria

Patients will be excluded from study entry if any of the following exclusion criteria exist at screening:

1. Known hypersensitivity to PGZ.
2. Infection at the time of presentation as defined by body temperature $> 38^{\circ}\text{C}$, pneumonia evident on chest X-ray, urinary tract infection (positive tests for nitrites, leukocyte esterase, and bacteria on urine analysis), other acute infection per history or current use of antibiotic or antiviral treatment.
3. Active malignancy and / or autoimmune disease requiring treatment.
4. Use of immunomodulatory drugs or chemotherapy.
5. History of stroke or brain injury within the last 90 days prior to presentation.
6. Acute illness within the last 30 days which could have affected the white blood cell count.
7. Known history of clinically significant hypoglycemia.
8. Patients already taking PGZ.
9. Active liver disease (ALT and /or AST 2.5 times the upper limit of normal, total bilirubin > 1.2 mg/dl).
10. Acute decompensated heart failure, and/or admission for an acute coronary syndrome, myocardial infarction (MI), cardiac arrest, coronary artery surgery within the past 3 months and patients with New York Heart association Class III and IV heart failure.
11. History of bladder cancer
12. Pregnant and nursing women.
13. Currently incarcerated patients.

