7.4 Test Article(s) (Study Drug(s) and/or Study Device(s))

7.4. 1 Description

Pioglitazone hydrochloride 45mg tablets will be overencapsulated to match placebo capsules for this study.

Pioglitazone, a peroxisome proliferator-activated (PPAR γ) receptor agonist, is FDA-approved as an anti-glycemic agent for the treatment of type-2 diabetes that has shown promise for secondary stroke prevention in clinical stroke trials [3-5], but has thus far not been studied as an acute intervention for acute diabetic stroke. PGZ acts primarily by decreasing insulin resistance.

7.4. 2 Treatment Regimen

Following oral administration, PGZ is first measurable in serum within 30 minutes, with peak concentrations observed within 2 hours. It is relatively insoluble but can be crushed and given through a feeding tube. Serum concentrations of total PGZ (PGZ plus active metabolites) remain elevated 24 hours after a once daily dosing.

The treatment group will receive 45 mg of PGZ orally within 18 hours of stroke symptom onset or last known well and subsequently at 24h and 48h after the initial dose. This represents the highest recommend dose in humans and is selected to achieve the highest blood concentration of PGZ as quickly as possible following the stroke event. The control group will receive placebo orally at the same time points. Both groups will be treated identically and receive best standard of care.

Some acute ischemic stroke patients experience trouble swallowing (dysphagia), and all stroke patients are therefore routinely assessed for dysphagia as part of their routine clinical care. If patients are not able swallow, PGZ/placebo will be crushed and administered via a feeding tube.

To avoid unblinding of the study team if the capsules have to be opened/crushed for administration, a warning label will be placed on study drug package telling the bedside nurse not to reveal the contents of the capsule to study team members. Study team members will not administer drug to any patients who are unable to swallow.

There is no provision to provide study treatment after the study.

7.4. 3 Method for Assigning Subject to Treatment Groups

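### Exclusion 8 bars prior pioglitazone (PGZ) but no other drug of its class, so a patient already exposed to the mechanism under test could be randomized; cheap to close, and probably small in effect

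*Combined protocol and SAP*

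**What the plan says.** Section 3.2, item 8, excludes "Patients already taking PGZ". Item 4 of the same list excludes "Use of immunomodulatory drugs or chemotherapy"; the term is not defined and no antidiabetic drug is mentioned.

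Section 2.2 gives the preclinical case. It reports that "darglitazone, that is a similar drug within the same class and similar mechanism of action, restores the altered pro-inflammatory response", and that this drug "dramatically reduces stroke size in diabetic ob/ob mice when administered before IS was induced". For the study drug itself it reports that "PGZ given to non-diabetic C57BL6 mice within 2h after acute IS, also reduced the stroke size". Section 7.4.1 describes PGZ as a PPAR-gamma agonist that "is FDA-approved as an anti-glycemic agent for the treatment of type-2 diabetes".

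Other sections that bear on prior or concurrent drugs:

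- Section 3.3.1 removes patients who come to need immunomodulatory drugs, or who newly meet an exclusion criterion during treatment.
- Section 7.4.6.5 has concomitant drugs recorded daily and sets rules only for CYP2C8 inhibitors and inducers.
- Section 7.2.1 collects current medication at baseline.
- Section 7.4.3 describes 1:1 allocation in permuted blocks and states no stratification factor.
- Section 8.3 lists no covariate for prior medication.

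**The concern.** The plan treats class and mechanism as relevant evidence when it argues that PGZ should work, but treats only the single molecule as relevant when it decides who is already exposed. Several other exclusions (infection, treated autoimmune disease, immunomodulatory drugs, recent illness affecting the white cell count) keep out patients whose immune markers are disturbed before dosing. Prior exposure to another drug with the mechanism under test is the same kind of disturbance, and exclusion 8 covers only part of it.

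Two things are at stake. A class user on placebo may be partly treated, and the pre-dose blood sample, which is the baseline for the biomarker profiles, may already be shifted. A class user on PGZ may have overlapping exposure, which would make it harder to attribute the hypoglycemia and fluid retention listed as risks in section 10. Section 8.2 says the pilot data will feed the power analysis of a later trial, so any dilution would carry forward into that calculation.

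**Working it through.** **Step 1: does any written rule keep out a user of another class drug?**

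- Exclusion 8: no. It names one drug.
- Exclusion 4: not clearly. If immunomodulatory drugs were meant to include this class, the separate item for PGZ would be redundant. Section 3.3.1 would also sit badly with the trial, since it removes patients who need immunomodulatory drugs and the trial gives PGZ.
- Section 3.3.1: no. Apart from immunomodulatory drugs, it refers back to the same exclusion list.
- Section 7.4.6.5: no. It records drugs and regulates only those acting on CYP2C8.
- Sections 7.2.1, 7.4.3 and 8.3: the information is collected, but it is neither a stratification factor nor a model term.

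So such a patient is eligible on the wording.

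**Step 2: how large could the effect be?** The plan states no alpha, power, effect size or frequency of class use, so there is no figure to reproduce. What follows is illustration.

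*Per patient.* Inputs: 25 per arm (section 8.2). Assumption: the prior drug gives the full PGZ effect and no more, and added PGZ gives nothing further. One such placebo patient then moves the placebo mean by 1/25 of the true contrast, which is 4%. Two move it by 2/25 = 8%. With the 22 per group that section 8.2 targets for analysis, one patient is 1/22 = 4.5%. A smaller effect of the prior drug gives less dilution.

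*By share of class users.* Let f be the share of patients on another class drug (assumed, 1% to 20%). The contrast is multiplied by (1 − f). The chance of at least one such placebo patient is 1 − (1 − f)^25. For power, assume two-sided 0.05 and the contrast that would have 80% power undiluted:

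d = (1.960 + 0.842) × √(2/25) = 0.792 SD

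Power = Φ(d(1 − f) × √(25/2) − 1.960)

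| f (assumed) | Expected among 25 placebo | Chance of at least one | Power |
|---|---|---|---|
| 0 | 0 | 0 | 80.0% |
| 1% | 0.25 | 22% | 79.2% |
| 2% | 0.5 | 40% | 78.4% |
| 5% | 1.25 | 72% | 75.9% |
| 10% | 2.5 | 93% | 71.3% |
| 20% | 5 | above 99% | 61.1% |

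The loss is negligible at 1% to 2% and material only from about 10%. Nothing in the documents indicates where in this range, or below it, the true share lies.

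**The case against.** The strongest objection is that the documents do not show that any such patient exists. The only other class member they name is darglitazone, given to mice. They give an approved indication for PGZ alone and no prescribing data. That stands: the frequency is unknown and may be zero, and the point concerns what the wording permits.

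A reader might infer that the plan credits the whole class with a pre-stroke benefit, or that a patient on another class drug is in the same position as the pre-dosed animals. Section 2.2 does not support either reading. Its pre-stroke evidence is one compound in diabetic mice, and PGZ itself was given after the stroke to non-diabetic mice. A reader might also infer that patients in the PGZ arm would receive two drugs of the class. That holds only if the home drug is continued in hospital, which the documents do not say; the glucose-care protocols in Appendix 1 are not in the text available.

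Exclusion 4 might be read by the investigators as covering the class. If so, the gap closes in practice, but the plan should say so, and the separate PGZ item points the other way.

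On safety, sections 9.1, 10 and 18.7 already provide glucose checks, heart failure monitoring, rules for stopping treatment and an independent safety monitor. These limit the safety side of the concern but do not address the mixed exposure in the comparison. Finally, prior medication is recorded, so class users could be identified afterwards. That helps, although with 25 per arm an adjusted or restricted analysis is a weaker remedy than a clear entry rule.

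**Conclusion.** The point holds as a low-severity, cheap improvement. Exclusion 8 is narrower than the reasoning in section 2.2, and no other rule clearly keeps out users of another class drug. The size is at most 4% dilution of the contrast per such placebo patient with 25 per arm, assuming that the prior drug does no more than PGZ would and that PGZ adds nothing to it. The number of such patients is not given and may be zero.

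It would be wrong to infer that the trial is biased in favour of PGZ. Allocation is randomized 1:1, so prior class use is balanced on average; the expected consequence is some attenuation and noise. In an exploratory pilot with no stated power, this does not threaten the design.

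**What to change.** Reconcile section 3.2 with section 2.2 by extending exclusion 8 to *patients already taking PGZ or any other drug of the same class (PPAR-gamma agonist)*. If the sponsor intends exclusion 4 to cover the class, it should say so there instead.

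The check needs no new data. Section 4.2.4 already has the medical record reviewed against the criteria before a patient is approached, and section 7.2.1 already collects current medication. The check belongs at the record review, because section 7.2.1 lists the medication data after the randomization step.

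The cost is one line in an amendment and at most a few lost candidates. Section 15.2 reports over 800 stroke-service admissions a year and more than 40% of acute ischemic stroke patients hyperglycemic at first evaluation, so recruitment of 50 is unlikely to suffer. If the sponsor prefers to keep exclusion 8 as it stands, section 8.3 should state how prior and concurrent class use will be reported and handled in the analysis.

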3.3 Early Withdrawal of Subjects

3.3. 1 Criteria for removal from study

Patients with a need for treatment with immunomodulatory drugs or those who develop any new conditions described in the exclusion criteria during treatment phase of clinical trial will be removed from the study. Additionally, cognitively impaired subjects will be withdrawn if they are unduly distressed as required by IRB policies.

3.3. 2 Follow-up for withdrawn subjects

Subjects will be withdrawn from the study if the study subject or Legally Authorized Representative (LAR) withdraws consent for any reason. The primary reason for the subjects' withdrawal from the study will be recorded.

If a subject is withdrawn due to pregnancy, experiences an adverse event (AE), a medical emergency, or is unwilling or unable to comply with the protocol, he/she must undergo a 90 day assessment unless the withdrawal is due to death or the withdrawal of consent. Subjects who withdraw from the study may be replaced.

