Precautions: PGZ is metabolized in the liver. Therefore, any drug which is a strong CYP2C8 inhibitor or inducer may affect the efficacy of PGZ. Subjects who require these medications during study drug treatment are permitted into the study with additional monitoring/precautions in place:

1. Strong CYP2C8 inhibitors (such as gemfibrozil) increase PGZ concentrations. Therefore, gemfibrozil will be held for the 3 day duration of the study treatment and started after 24 hours of the last dose of study drug.
2. CYP2C8 inducers (e.g., rifampin) may decrease PGZ concentrations. Therefore, these medications will be spaced 4 hours after administration of the study drug.

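### As written, section 3.3.1 may end research data collection, not only study drug, when a new exclusion condition arises during treatment; the intention-to-treat status of those patients is unstated

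*Combined protocol and SAP*

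**What the plan says.** Section 3.3.1, on removal from the study, states that "those who develop any new conditions described in the exclusion criteria during treatment phase of clinical trial will be removed from the study". It applies the same consequence to patients who need immunomodulatory drugs.

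Section 3.3.2 sets out what follows. For withdrawals due to pregnancy, an adverse event, a medical emergency or non-compliance, "he/she must undergo a 90 day assessment unless the withdrawal is due to death or the withdrawal of consent". No other visit or sample is required. It adds that "Subjects who withdraw from the study may be replaced".

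The exclusion list in 3.2 includes infection or antibiotic use (item 2), abnormal liver tests (item 9) and acute cardiac events (item 10). Item 2 opens with "Infection at the time of presentation as defined by body temperature" and ends with "other acute infection per history or current use of antibiotic or antiviral treatment".

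Sections 10.0 and 18.7 cover some of the same events. Both stop study drug for liver abnormality and for heart failure, and 18.7 does so for acute coronary events as well. Neither says that the patient leaves the study.

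Section 8.2 aims for 44 patients in an intention-to-treat analysis without defining the set. Section 8.3 models biomarkers over time by arm with linear mixed models and does not mention removed or replaced patients.

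**The concern.** The treatment period (72 hours, section 7.3) is the same window in which the three post-dose biomarker samples are drawn. If a patient leaves the study in that window and only a Day-90 assessment follows, the later samples and the discharge BI, GOS and MOCA are lost. Discharge NIHSS and mRS are not marked as research-only and may still be in the record.

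The loss would not be random if the trigger is something treatment can change. Section 10.0 lists liver dysfunction and heart failure as risks of PGZ. Section 11.1 names fewer infections as a possible benefit, and 1.1 collects infection as an outcome. Removal could therefore fall more heavily on either arm.

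The analysis most directly exposed is the biomarker-by-time comparison of the arms in 8.3, which serves secondary endpoint 1. The second primary objective, "to study whether there is association between immune-stress response modulation and clinical outcomes after treatment of PGZ", would have fewer data. Because 8.2 wants the pilot to inform a later power calculation, it also matters who is counted.

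**Working it through.** **Does 3.3.1 mean leaving the study?**

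- Section 3.3.1 speaks of the study, not of study drug. Section 7.4.6.4 refers to 3.3 when it describes a subject withdrawn from the study.
- Where the protocol means drug only (10.0, 18.7), it says so.
- No sentence says that draws stop on removal, and none says that they continue. Section 7.1 plans blood from all participants, but a removed patient is no longer clearly one. The loss is an inference from these texts.

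**Which events trigger it?**

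- Liver and cardiac events: 3.3.1 covers them through exclusions 9 and 10, while 10.0 and 18.7 stop study drug. The two consequences can coexist, but the protocol does not say whether they do.
- Infection: uncertain. Item 2 is tied to presentation and in-hospital infection is an outcome. Section 7.4.6.5 lists "CYP2C8 inducers (e.g., rifampin) may decrease PGZ concentrations" and says "Subjects who require these medications during study drug treatment are permitted into the study", which fits poorly with antibiotic use as a removal trigger. Against that, 3.3.1 reaches any new condition on the list.

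**Is Day 90 safe?** Mostly, if the removal also counts as an adverse event or medical emergency under 3.3.2. Need for immunomodulatory drugs is not a listed reason, so coverage is not certain.

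**The plan's own figure (8.2).** The 44 follows a predicted 3-month attrition of 18%, given as n=5. But 50 × (1 − 0.18) = 41 and 50 − 5 = 45, while 44 implies a loss of 6/50 = 12%. The 44 is not exactly reproduced, and the text gives no term for patients removed under 3.3.1 or replaced. The point here does not depend on this figure.

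**Loss per removed patient.** Inputs: 25 per arm (8.2) and three post-dose draws (7.2, 9.4), so 25 × 3 = 75 draws per arm and 150 in all.

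- Day-3 samples: 1/25 = 4% of the arm.
- Removal before the Day 1, 2 or 3 draw loses 3, 2 or 1 draws, that is 3/75 = 4.0% down to 1/75 = 1.3% of the arm's draws.
- The only scheduled on-treatment liver test is on Day 2, before the third dose, like that day's biomarker draw (7.2.3). A removal on its result would normally cost the Day 3 draw only.

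**Illustration under assumed rates (the documents give none).**

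- Chance of at least one removal in 50: at 2%, 1 − 0.98^50 = 0.636; at 5%, 1 − 0.95^50 = 0.923.
- At 5% to 20% removed in both arms, 2.5 to 10 patients leave. With timing spread evenly (on average 2 of 3 draws lost), 5 to 20 of 150 draws go (3.3% to 13.3%). The extremes are 2.5 × 1 = 2.5 draws (1.7%) and 10 × 3 = 30 draws (20%).
- Suppose 20% are removed in one arm and 10% in the other, and removed patients differ from retained ones by 0.5 to 1.0 SD in the same direction in both arms. A Day-3 comparison of retained patients is then off by (0.20 − 0.10) × 0.5 = 0.05 SD to (0.20 − 0.10) × 1.0 = 0.10 SD. The sign depends on which arm loses more. The standard error of a difference with 25 per arm is √(2/25) = 0.28 SD, so this is about 0.18 to 0.35 of one standard error.

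**The case against.** The best case for the plan has four parts.

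First, the text can be read benignly. Infection is meant to be counted, so infected patients probably stay in. For liver and cardiac events, the more specific sections only stop study drug, and 10.0 expects liver dysfunction and heart failure to be unlikely in so short a treatment. This stands as a reason for caution about how often the rule would bite. It does not remove the ambiguity, because 3.3.1 is worded to reach any new condition on the list.

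Second, several exclusions screen out conditions that disturb immune measures, and a sample taken after a new infection or immunomodulator partly measures that event. This is true, but it concerns how such samples are analysed. A sample that was collected can be set aside; one missed within 72 hours cannot be recovered.

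Third, the mixed models use samples taken before removal, and the triggering event is recorded as an adverse event (9.1). Both are correct. The models still rely on missingness being explained by observed data, which 8.3 neither states nor examines.

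Fourth, this is an exploratory pilot, and in the illustration above the bias is well below one standard error. That limits the weight of the point. It is not a reason to leave a rule that costs little to correct.

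A reader might also infer that 3.3.1 flatly contradicts 10.0 and 18.7, or that the protocol orders sampling to stop. The documents do not go that far: the boundary between stopping drug and leaving the study is unclear, and the end of sampling is inferred.

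**Conclusion.** The point holds in conditional form, as a cheap improvement. Followed as written, 3.3.1 with 3.3.2 permits removal after randomisation on events that treatment may affect, with no stated requirement to complete the remaining draws or the research-only discharge scales. The analysis status of removed and replaced patients is not given.

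The firm quantity is small: each removal costs 4% of an arm's Day-3 samples and 1 to 3 of that patient's post-dose draws. Everything beyond that rests on assumed removal rates, so neither the size nor the direction of bias can be stated.

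Three stronger conclusions are tempting and not supported. It cannot be said that infection will trigger removal, given the wording of exclusion 2 and the outcome list. It cannot be said that the Day-90 clinical comparison is lost, since 3.3.2 requires that assessment for most likely routes of removal. And the between-arm biomarker profile should not be presented as the primary comparison: it serves secondary endpoint 1, while primary objective 2 concerns an association and is affected mainly through fewer data.

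**What to change.** - **3.3.1 and 3.3.2:** State which new conditions the rule covers, and reword it so that a new exclusion condition does not by itself end study data collection. Keep the remaining scheduled draws (at nominal times from first dose), the discharge scales and the Day-90 assessment for every randomised patient, unless consent is withdrawn or IRB or legal requirements prevent it (for example undue distress or incarceration).
- **8.2:** Define the intention-to-treat set as all randomised patients in their assigned arm. Replacements are added to removed patients, not substituted for them.
- **8.3:** Flag samples taken after a new infection or immunomodulator, and allow a sensitivity analysis without them.
- **3.3.1 against 10.0 and 18.7:** Reconcile these on stopping study drug versus leaving the study. No clinical rule is proposed here.

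The cost is protocol wording plus a few draws and scales that are already scheduled, in patients off study drug. Under the assumed 5% to 20% removal this is about 3 to 30 draws and 3 to 10 discharge sets. Some of those samples will reflect the intercurrent event, which is why they should be flagged.
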